2.1.3 Recruitment Strategies

This study will be listed on available websites (www.clinicaltrials.gov, <https://ccr.cancer.gov/clinical-trials-search-start>) and participants will be recruited from the current patient population at NIH and participating sites.

2.2 SCREENING EVALUATION

- A. Pathological confirmation of diagnosis by either the Laboratory of Pathology at the NIH, Walter Reed National Military Medical Center, MSKCC, DFCI, or BIDMC may

be obtained anytime prior to enrollment (if specimen is available). If no pathologic specimen is available, patients may enroll with a pathologist's report showing a histologic diagnosis of prostate cancer and a clinical course consistent with the disease.

- B. The following parameters will be obtained within 8 weeks prior to enrollment:
 - 1. HIV test
 - 2. Hepatitis B and C
 - 3. Tc-99 whole-body scintigraphy
 - CT (or MRI may be substituted at investigator's discretion) of chest, abdomen and pelvis
- C. The following parameters will be obtained within 16 days prior to enrollment (cycle 1 day 1 for immediate treatment arm [Arm A], or M-6 visit for surveillance first arm [Arm B]):
 - 4. History and physical examination with ECOG
 - 5. Serum PSA
 - 6. Complete blood count plus differential and platelet count
 - 7. Hepatic and Acute Care
 - 8. Testosterone level

2.3 REGISTRATION PROCEDURES

Authorized staff must register an eligible candidate with NCI Central Registration Office (CRO) within 24 hours of receiving a signed consent. A registration Eligibility Checklist from the web site (<http://home.ccr.cancer.gov/intra/eligibility/welcome.htm>) must be completed and sent via encrypted email to: NCI Central Registration Office [contact]. After confirmation of eligibility at Central Registration Office, CRO staff will call pharmacy to advise them of the acceptance of the patient on the protocol prior to the release of any investigational agents. When relevant, treatment assignment is conveyed to the Pharmacy at the same time. Verification of Registration will be forwarded electronically via e-mail to the research team. A recorder is available during non-working hours.

2.3.1 For Participating Site Registration

Registration will be a two-part process as patients are screened on this protocol. A protocol registration form will be supplied by the NCI study coordinator and updates will be provided as needed. Subject eligibility and demographic information is required for registration. To initially register a subject, after the participant has signed consent, complete the top portion of the form and send to NCI study coordinator. Once eligibility is confirmed, after completion of screening studies, complete the remainder of the form which is the eligibility checklist, indicating that the patient is being registered for treatment and send to NCI study coordinator. In addition, source documents supporting the eligibility criteria must be sent to the NCI study coordinator. The NCI study coordinator will notify you either by e-mail or fax that the protocol registration form has been received which will include the unique patient/subject ID number. Questions about eligibility should be directed to the NCI study coordinator or NCI PI. Questions related to registration should be directed to the NCI study coordinator.

Subjects that do not meet screening criteria should be removed from the study following the procedure in section **3.7.3**.

2.3.2 Treatment Assignment and Randomization Procedures

Cohorts

Number	Name	Description
1	Prostate Cancer	Male patients diagnosed with prostate cancer (non-metastatic), with demonstrated biochemical progression, a PSA doubling time of 5-15 months, and with a rising PSA.

Arms

Letter	Name	Description
A	PROSTVAC treatment	PROSTVAC treatment for 6 months with an additional optional year of maintenance for eligible patients
B	Delayed PROSTVAC treatment	Surveillance for 6 month followed by PROSTVAC treatment for 6 months with an additional year of maintenance for eligible patients

Randomization and Arm Assignment

Subjects in Cohort 1 will be randomized on a 1:1 basis to **Arm A** or to **Arm B**. The computerized randomization will be performed by the NCI Central Registration Office. CRO staff will send a secured e-mail with the Verification of Registration of the patient and treatment arm patient is randomized to. This process will be completed within 15–30 minutes of sending the eligibility checklist. CRO will keep track of all randomization data in Clinical Data Registry (CDR) of CRO.

2.4 BASELINE EVALUATION

- A. The following parameters will be obtained **within 8 weeks** prior to treatment initiation:
 1. Baseline electrocardiogram (EKG) on all patients, and appropriate cardiologic evaluation, as clinically indicated, to provide baseline function and identify any patients who should be monitored closely for cardiac risks associated with vaccinia vaccination.
- B. The following parameters will be obtained **within 16 days** prior to start of treatment (these tests will not need to be repeated if they were done at screening within the appropriate timeframe):
 1. Clinical evaluation
 - History and physical examination
 - ECOG performance status (see **APPENDIX A**)
 - Height, weight

2. Laboratory studies

- Serum PSA
CBC/differential, with platelet count
- Serum testosterone level
- Serum chemistries (Na⁺, K⁺, Cl⁻, CO₂, glucose, BUN, creatinine, albumin, calcium, magnesium, phosphorus, alkaline phosphatase, ALT, AST, total bilirubin, LDH, CK, uric acid, total protein)
- Lymphocyte phenotyping CD3/CD4/CD8
- Urinalysis in patients unless no feasible (i.e. patient has incontinence)
- PAP (prostatic acid phosphatase), at the discretion of the PI

3 STUDY IMPLEMENTATION

3.1 STUDY DESIGN

- This is a randomized trial of PROSTVAC for 6 months vs. surveillance for 6 months followed by PROSTVAC for 6 months in patients with nmCSPC prostate cancer. 72 evaluable patients will be enrolled with an accrual ceiling of 110 patients
- PROSTVAC will be administered identical to the Phase III dosing with vaccine given week 1 (vaccinia-PROSTVAC, 2x10⁸ infectious units subcutaneously) and then fowlpox-vaccine (1x10⁹ infectious units subcutaneously) on weeks 3 and 5 followed by monthly fowlpox-vaccine (1x10⁹ infectious units subcutaneously) for a total of 5 months (including vaccinia, vaccine is administered over 6 months).
- The primary endpoint of this trial will be to determine if PROSTVAC can decrease tumor growth rate as measured by PSA rise after 6 months compared to a group getting surveillance alone. This time frame should be sufficient to evaluate immune effect on the re-growth rate given that the ECOG 9802 analysis demonstrated a significant change in tumor growth rate after starting PROSTVAC.
- Secondary endpoints include observing the effects of vaccine on PSA growth rate when prostvac is initiated after 6 months of surveillance, immune response evaluation will include CD4 cells, CD 8 cells, PSA-specific T-cells, natural killer cells, Regulatory T-cells, Regulatory T-cell function, cytokines, naïve thymic emigrants, associate immunologic outcomes with PSA responses/changes in growth rates.
- For patients who have a PSA doubling time greater than 5 months (measured over the previous 6 months of treatment), they may receive maintenance vaccine every 3 months for an additional year. For patients who are on-study at the time of this amendment, they will be given an option to receive 1 year of vaccine maintenance (4 doses, administered every 3 months).
- When possible, patients will be followed for TTP beyond the treatment period.

3.1.1 Protocol Stopping Rules

This study will utilize the Common Terminology Criteria for Adverse Events (CTCAE) version 4.0 for grading systemic toxicity (see section [6.3](#)).

- One occurrence of grade 5 toxicity by the NCI-CTCAE version 4.0 attributable to the treatment regimen.
- Two occurrences of grade 4 toxicity by the NCI-CTCAE version 4.0 attributable to the treatment regimen.

If either of the above occurs, the Principal Investigator will halt accrual to the trial and will discuss with the NCI Institutional Review Board (IRB) whether any changes need to be made to the protocol.

3.2 DRUG ADMINISTRATION

Patients will receive PROSTVAC identical to Phase III dosing (NCT01322490) which consists of a single immunization of PROSTVAC-V (vaccinia-PROSTVAC, 2×10^8 infectious units subcutaneously) in Week 1, followed by immunizations of PROSTVAC-F (fowlpox-PROSTVAC 1×10^9 infectious units subcutaneously) administered on weeks 3 and 5 followed by monthly fowlpox-vaccine (1×10^9 infectious units subcutaneously) for a total of 5 months (including vaccinia, vaccine is administered over 6 months).

The preferred PROSTVAC-V/F subcutaneous injection site is the upper thigh. If given on the arm, which is not preferred, the vaccine should be administered subcutaneously in the back of the upper arm.

3.3 TREATMENT MODIFICATIONS

3.3.1 Vaccine

3.3.1.1 Dosing delay

- Patients must have recovered to \leq grade 1 toxicity related to vaccine (or baseline) for the parameters used to assess levels of organ function required for eligibility (see Section 2.1) after each vaccination in order to receive a subsequent vaccination.
- If \geq grade 2 nonautoimmune toxicity attributable to the vaccine persists for > 42 days, the patient will not receive further vaccine inoculations and will be removed from the protocol treatment and followed for resolution of toxicity and immune endpoints.
- Patients who develop grade 3 injection site reactions will have their vaccine held until injection site reaction resolves to grade 2 or less.
- Patients who develop \geq a grade 2 allergic or autoimmune disease that threatens vital organ function or any \geq grade 3 autoimmunity, not related to a therapeutic response, will be removed from the protocol treatment and followed for resolution of toxicity and immune endpoints.
- Patients who develop any grade 4 toxicity attributable to the study drug(s) will be removed from the protocol treatment and followed for resolution of toxicity and immune endpoints.
- If a scheduled vaccine dose is missed due to scheduling or logistical issues, the vaccine may be given within 14 days of the appointed time

3.3.1.2 Dose modifications

No dose modifications are allowed with this vaccine.

3.4 QUESTIONNAIRES

3.4.1 Evaluating Quality of Life in this Population

Little has been formally evaluated about the impact of PSA kinetics on patients with BCR. Beginning with amendment G, patients enrolled onto either the immediate vaccine arm or the surveillance followed by vaccine arm will be asked to complete a prostate cancer specific QOL survey with 18 questions (MAX-PC) as well as the FACT-P survey at the following time points:

Immediate vaccine Arm

Baseline; 3 months; 6 months; 9 months; approximately q3-4 months in follow-up

Surveillance Arm

-6 months; -3 months; Baseline/start of vaccine; 3 months; 6 months; 9 months; approximately q3-4 months in follow-up

Each survey will take approximately 5 minutes to complete and they will be administered in english. The surveys being used have been published and vetted as appropriate QOL tools²¹⁻²³. This analysis will be done in an exploratory fashion as part of a collaboration with [name] who is an expert in prostate cancer QOL studies.

3.5 PROTOCOL EVALUATION (SEE APPENDIX C)

3.5.1 All patients who are deemed eligible and who sign an informed consent will be enrolled in this trial.

3.5.2 A complete history and physical examination, including ECOG performance status, will be done within 16 days before enrollment.

3.5.3 Laboratory Studies

(See also APPENDIX C)

- Serum PSA
- CBC/differential with platelet count
- Serum testosterone level
- Serum chemistries (Na⁺, K⁺, Cl⁻, CO₂, glucose, BUN, creatinine, albumin, calcium, magnesium, phosphorus, alkaline phosphatase, ALT, AST, total bilirubin, LDH, CK, uric acid, total protein)
- HIV/Hepatitis B/Hepatitis C tests (within 8 weeks prior to start of enrollment)
- Lymphocyte phenotyping CD3/CD4/CD8

3.5.4 Radiographic assessment

Patients will undergo scheduled radiographic assessment for metastatic disease at 6 month intervals. Radiologic studies consisting of bone scan, CT scan of chest, and CT scan of abdomen/pelvis will be performed at baseline. MRI may be substituted for CT scan at the discretion of the investigator.

Patients in this trial may have the option to take part in a PET imaging study at the NIH in Bethesda, MD, which may utilize relevant data from this study.

3.5.5 Assessment for PROSTVAC administration

Dosing and administration of PROSTVAC will be performed in the NIH Day Hospital, MSKCC, DFCI, or BIDMC. Patients will be monitored with vital signs (blood pressure, heart rate, respiratory rate, temperature) prior to and within 1 hour after the initial vaccine treatment. On subsequent visits (where rF-PROSTVAC is administered) patients will have vital signs checked prior to vaccine and then be monitored for 30 minutes after vaccine treatments. (Post-vaccine vital signs will not be required except for the first vaccination.) Documentation of any patient reported symptoms occurring between dosing will be included in the assessment. Laboratory assessments will be conducted as per **APPENDIX C**.

3.6 CONCURRENT THERAPIES

Concurrent hormonal therapy will not be allowed. Concurrent anticancer treatment with chemotherapy, systemic glucocorticoids (topical and inhaled steroids allowed), radiation therapy, major surgical procedures for prostate cancer, and nonprotocol-related immunotherapy will not be permitted.

Concurrent systemic corticosteroid use (daily or every other day for continued use > 14 days) will also not be allowed.

3.7 CRITERIA FOR REMOVAL FROM PROTOCOL THERAPY AND OFF STUDY CRITERIA

Prior to removal from study, effort must be made to have all subjects complete a safety visit approximately 28 days following the last dose of study therapy.

3.7.1 Criteria for removal from protocol therapy

Patients will be removed from treatment for the following:

- Clinical or radiographic progression of disease.
- Grade 3 or greater toxicity attributed to treatment that does not resolve to grade 1 within 42 days from time of scheduled treatment.
- Grade 2 or greater autoimmune disease that threatens vital organs.
- Any Grade 4 toxicity that is possibly, probably or definitely related to the protocol treatment will require a patient to be off-treatment
- Intercurrent illness or medical circumstances. If at any time the constraints of this protocol are detrimental to the patient's health, the patient may be removed from protocol therapy and reasons for withdrawal will be documented.
- Any grade of seizure will require a patient to be off-treatment.
- Requirement for androgen deprivation therapy
- Completion of protocol therapy including an approximately 28 day safety visit as outlined in section **3.8** (when logistically feasible)

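### Sections 3.3.1.1 and 3.7.1 both set mandatory criteria for ending vaccine, but differ on toxicity grade, the 42-day clock, and the allergic and autoimmune triggers

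*Combined protocol and SAP*

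**What the plan says.** Section 3.3.1.1 (Dosing delay) covers more than delay. Its persistence rule starts at grade 2: where "grade 2 nonautoimmune toxicity attributable to the vaccine persists for" more than 42 days (the text sets the grade as a minimum), "the patient will not receive further vaccine inoculations and will be removed from the protocol treatment". A second rule covers patients who develop at least "a grade 2 allergic or autoimmune disease that threatens vital organ function or any" autoimmunity of grade 3 or higher; that sentence ends "grade 3 autoimmunity, not related to a therapeutic response, will be removed from the protocol treatment". A third rule is that any "grade 4 toxicity attributable to the study drug(s) will be removed from the protocol treatment".

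Section 3.7.1 (Criteria for removal from protocol therapy) is also worded as mandatory. Its persistence rule is "Grade 3 or greater toxicity attributed to treatment that does not resolve to grade 1 within 42 days", counted from the scheduled treatment. Its autoimmune rule is "Grade 2 or greater autoimmune disease that threatens vital organs". It also lists any related grade 4 toxicity, a seizure of any grade, and a discretionary item for intercurrent illness or medical circumstances.

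Neither section refers to the other or says which governs. Section 3.8 (Follow-up Evaluations) ties the post-treatment safety visit to stopping for a reason listed in section 3.7.

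**The concern.** Both sections direct removal from protocol treatment, so a reader expects the same triggers in both. They differ in the grade at which persistent toxicity counts, in when the 42 days start, and in what autoimmune or allergic event is enough.

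The stake is consistent application of a safety rule. Section 3.5.5 has vaccine given at four places (NIH, MSKCC, DFCI and BIDMC). A site that looks under the heading on removal criteria finds one set of triggers; a site that works from the dosing-delay rules finds another. Sections 7.2.1 and 7.3.2 make every protocol deviation reportable, and a site reading 3.7.1 alone would not recognise a missed 3.3.1.1 removal as a deviation. Arm A receives vaccine at once and Arm B after six months, so both arms are exposed to the ambiguity.

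**Working it through.** No arithmetic in the plan bears on this. The check sets the rules side by side and runs hypothetical patients through each.

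| Element | Section 3.3.1.1 | Section 3.7.1 |
|---|---|---|
| Persistent toxicity, lowest grade | 2 (non-autoimmune) | 3 (any attributed toxicity) |
| 42-day clock | Duration of the toxicity | From the scheduled treatment |
| Autoimmune, vital organs threatened | Grade 2 or higher | Grade 2 or higher |
| Allergic, vital organs threatened | Grade 2 or higher | No specific trigger |
| Other autoimmunity | Any of grade 3 or higher | No specific trigger |
| Exception for therapeutic response | Yes | No |
| Related grade 4 | Remove | Remove |
| Seizure, any grade | Not listed | Remove |

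Hypothetical patients:

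1. Non-autoimmune vaccine toxicity, grade 2 throughout, lasting 50 days. Section 3.3.1.1: grade 2 is reached and 50 > 42, so removal is required. Section 3.7.1: the grade never reaches 3, so no toxicity criterion is met.
2. Grade 3 autoimmunity, unrelated to a therapeutic response, no vital organ threatened, back to grade 1 within 42 days. Section 3.3.1.1: removal required. Section 3.7.1: not required, because the event resolved in time and is neither grade 4 nor a threat to vital organs.
3. Grade 2 allergic disease threatening vital organ function. Section 3.3.1.1: removal required. Section 3.7.1: not required, because its organ-threat item names autoimmune disease only.
4. Treatment-attributed grade 3 autoimmunity judged related to a therapeutic response, no vital organ threatened, not down to grade 1 within 42 days. Section 3.3.1.1: exempt from the autoimmune rule, and outside the persistence rule because that covers non-autoimmune toxicity. Section 3.7.1: removal required. Here the mismatch runs the other way.

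The clock. Section 3.7.1 does not say which scheduled treatment starts the 42 days. Suppose it means the next scheduled dose (an assumption), and take the 28-day cycles of Appendix C. A toxicity of grade 3 that begins just after one dose reaches the limit about 42 days later under 3.3.1.1 and about 28 + 42 = 70 days later under 3.7.1, a gap of up to about 70 − 42 = 28 days. If it means the dose already given, the 3.7.1 clock starts at or before onset and the gap reverses.

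The grade 4 rules and the autoimmune trigger for threatened vital organs are essentially the same in both sections. The mismatch is confined to the other rows.

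**The case against.** The strongest reply is that the lists add up. Section 3.7.1 does not claim to be exhaustive, and nothing in it tells a site to go on dosing. A site that follows the whole protocol removes any patient who meets either list. A reader might infer that the same patient is removed under one section and kept on vaccine under the other. The documents do not support that: in cases 1 to 3, section 3.7.1 merely fails to require removal, and its medical-circumstances item permits it.

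The autoimmune and allergic gap is also narrower than a comparison of single items suggests. The grade 3 persistence item and the grade 4 item in 3.7.1 would catch some of these events. Two further safeguards help. The re-dosing condition in 3.3.1.1 withholds the next dose until vaccine toxicity is back to grade 1 or baseline, but only for the organ-function parameters used for eligibility. Section 7.7.1 has the coordinating team review adverse events weekly and by calls with the sites every 6 weeks, which makes unnoticed divergence less likely.

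These points limit the consequences but do not reconcile the text. Section 3.8 treats section 3.7 as the place where reasons for stopping are listed, and a patient removed only under 3.3.1.1 has no specific toxicity reason there. The medical-circumstances item says that a patient may be removed, which is weaker than the mandatory wording of 3.3.1.1. Adding the lists together would leave the grade 3 item largely redundant for non-autoimmune toxicity, and would settle neither the clock nor the therapeutic-response exception.

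A reader might also infer that the mismatch changes who is evaluable at month 6. That is not shown. Section 8 asks only for a growth-rate value from 0 to 6 months. Section 1.2.7.1 attempts a fit with more than one data point, and Appendix C schedules PSA at each cycle. Removal from therapy is separate from going off study: section 3.7.2 does not list toxicity. One of its reasons does start from being off treatment, but it also needs the patient's agreement to be followed on another protocol.

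**Conclusion.** The inconsistency is real. Sections 3.3.1.1 and 3.7.1 both state mandatory removal criteria and differ on the persistence grade, the start of the 42 days, the allergic trigger, the grade 3 autoimmune trigger and the therapeutic-response exception. Some patients who must be removed under 3.3.1.1 meet no mandatory criterion in 3.7.1, and at least one type of patient falls the other way.

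The number affected is unknown. The documents give no rate of persistent grade 2 toxicity, and section 1.2.3 describes the common side effects as grade 1, so it may be small. No power, sample-size or primary-analysis figure changes. The conclusion rests on the wording alone and assumes no event rate. The 28-day figure for the clock depends on reading the scheduled treatment as the next dose. The point should be corrected because it concerns a safety rule applied at four sites, not because of its expected frequency.

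**What to change.** Reconcile the two passages into one list of toxicity criteria for removal, and have the other section refer to it. The list needs one grade threshold for persistent toxicity, one stated start for the 42-day clock, and one rule for autoimmune and allergic events that says whether the therapeutic-response exception applies and to which events. Items that now stand in only one section, such as seizure, should be placed in the list deliberately. The reference in section 3.8 should then lead to it. Which rule stands is for the clinical leads to decide; this review takes no view.

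The cost is protocol wording in an amendment. No data collection, analysis or sample-size figure changes.

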3.7.2 Off-Study Criteria

- Patient is off-treatment and has agreed to be followed on a long term therapy protocol
- Patient requests to be taken off study. Reasons for withdrawal will be documented.
- Noncompliance with protocol guidelines (patient removed at discretion of Principal Investigator).
- Death
- Screen failure

